level of pain". The VAS scale will be used for both the SOC and intervention group to compare the pain level when starting the return line. The RN will collect a CBC before the start of the procedure which will be used in the programing of the TAP procedure. The RN will start recording the "inlet rate, return line pressures, and alarms" every 15 minutes until the procedure is completed.

Before patient disconnects, and after the completion of procedure sing the same therapeutic apheresis procedure access site, a blood sample will be drawn by the RN 2 lavender top tubes (4ml) for plasma hemoglobin test. The plasma hemoglobin test will be sent to the UTSW lab for analysis of hemoloysis and results will be sent back directly to the PI. Blood sample results will be collected by the PI or the study team in an excel spreadsheet (CRF) that will be saved on a secure drive on the UTSW campus.

Hemolysis is defined as the destruction of red blood cells which leads to the release of hemoglobin from the red blood cells into the blood plasma. Each patient will be tested for hemolysis by running plasma hemoglobin test after the procedure has finished. This will be collected in a two lavender tops (4ml) The cost for this test is covered by sponsor and because the patient has an indwelling access to venous blood there will no charge for drawing the sample.. There is no clinical suspicion that the use of the 20-gauge BD Nexiva Diffusics Catheter will increase this risk. Hemolysis will be scored dichotomously as present or absent for each encounter.

Pain is defined as any increase discomfort experienced by the patient associated with the apheresis procedure. The current standard of care is to ask the patient "are you having pain" and then ask them to rate the pain from 0 to 10. For this study, one additional question will be asked after the patient's vein has been accessed (IV catheter in place). The patient will self-report their pain using a 100 mm VAS scale. "*The VAS has been used by healthcare providers to measure the characteristics of disease severity in each patient individually*"(Klimek et al., 2017) Currently, all peripheral apheresis patients have some pain/discomfort while having a treatment, however; it is usually tolerated with minimal complaints.

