Measures of Quality of Apheresis will include inlet rate, and return pressures, procedure time. These measures are all readily available in the electronic medical record (EMR) and are all currently recorded as standard of care. The inlet rate is defined as the percent of patient inlet rate divided by the maximum allowable inlet rate. Because inlet rates are different for each type of TAP has a different maximum inlet rate, this will allow standardization across procedures. The max inlet rate for Photopheresis is 50ml/sec, the max inlet for plasma exchange is 100ml/sec inlet for red blood cell exchange is 55ml/sec. In addition, the inlet rate for each participant in the intervention arm will be compared to the average of their last 5 procedures. This measure will compare the efficiency of the SOC verses the intervention.

Inclusion Criteria

- Adult (≥ 18 years old)
- Speaks and reads English
- A patient of the Apheresis clinic at UT Southwestern University Hospital and Clinics
- Scheduled to receive TAP (therapeutic plasma exchange, red blood cell exchange and extracorporeal Photopheresis) as standard of care

Exclusion Criteria

- Prisoners
- Persons under the age of 18 years
- Patient who are actively involved in chemotherapy

Sources of Research Material

There are three sources of data for this study: electronic medical record (EMR) and paper-and-pen data collection from the patient's bedside (Data Collection form), and lab results provided by the UTSW laboratory via EMR. The EMR data that will be collected will include demographic information such as: age, sex, race, ethnicity, and admission diagnosis. The paper-and pen-data collection will include the patient self-reported pain level (VAS Scale), CBC collection, procedure data (minutes, inlet rate, return line pressures and alarms) total procedure time and post procedure sample. The paper-and-pen data collection form (Appendix 1) will record data only during patients TAP's encounter. Blood sample will be obtained from a SOC line. An additional 8 ml's for blood will be drawn from the patients for research purposes. Results from the bloodwork will be provided by the UTSW laboratory via the patient's EMR.

Recruitment Methods and Consenting Process

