For this study, patients will be recruited from the Apheresis Unit at UT Southwestern University Hospital and Clinics by a member of the research team. A member of the research team will screen the electronic medical record to determine a patient's eligibility. If a patient appears eligible for the study a member of the research team will discuss eligibility criteria with a member of the clinical team (nurse manger, nurse, physician, resident, fellow, social worker). The researcher will communicate with the clinical team to ensure eligibility: adult (≥18 years old), speaks and reads English, admitted to the Apheresis Unit at UT Southwestern University Hospital and Clinics at the time of consent. All patients in this study will be able to provide selfconsent (read and speak English).

When a patient is deemed eligible, a member of the research team will discuss consent and study procedures with that patient, in a place that is comfortable for the patient. After being approached by a member of the research team, patients will have up to next visit to consider participation in the study. The study team expects recruitment of 30 participants to last approximately 8 months. (Table 1)

Potential Benefits

There may or may not be a direct benefit to the participants in this study. Any additional blood test result that seems out of the norm will be shared with the nurse on duty or treating physician. We would also hope to share this with the greater research and clinical community in hopes of finding an alternative way for apheresis patients to have therapeutic apheresis procedures with less pain and no increase in adverse events.

Potential Risks

Risks associated with BD Cather:

Longer procedure time might occur if the inlet rate of the treatment is slower. The patient will be informed of this during the ICF process. With smaller catheters there's a risk of not obtaining the appropriate return rate for the patient. When the return rate is out of the SOC parameters the SOC apheresis equipment (Optia or Cellex) will alarm. If the alarm sounds 3 times the RN will decrease inlet rate by 5 ml/sec until the minimum threshold is reached (if needed), which is 50 ml/sec for plasma exchange and 35 ml/sec for RBC exchange and 20 ml/sec for photopheresis. If the alarm continues to when the minimum threshold is reached the catheter will

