efficacy wherein efficacy is represented by 1) the plasma hemoglobin value, and 2) the amount of time (minutes) required to complete a TAP. Hence models will be constructed to compare the mean plasma hemoglobin values by group, and to compare the mean number of minutes to complete TAP by group. Second, ANOVA will be used to compare the mean number of adverse events subjects experience in each group (intervention vs control).

Finally, a planned secondary analysis is to examine if the percent of lumen occupied by the return catheter is associated with return pressures. The suggested standard is that a catheter occupies < 45% of the inner-lumen diameter (measured with ultrasound). Return pressures >400 mm Hg are considered problematic. Chi-square analysis will be used to explore the odds of experiencing a return pressure > 400 mm Hg when the return catheter occupies <45% of the inner-lumen diameter.

Item	Month 1-2	Month 3-6	Month 4-8	Month 9-11	Month 12-18
IRB approval	Х				
Consent/	Х	X			
Enrollment					
Randomization	Х	X	Х	Х	
Data collection	Х	Х	Х	Х	
Manuscript				Х	X
prep					
Study closeout					X

Project Timeline

Enrollment of first patient (month 1), enrollment of the last patient (month 12), completion of data analysis (month 14), and manuscript submission (month 18). The apheresis team see approximatley 3000 TAP treaments each year. Of these, approximately 1500 encounters will meet the primary inclusion criteria. We anticipate that it will take less than 1-year to complete the study.

Future directions

The intention of this pilot study is to test the 20-gauge BD Nexiva Diffusics Catheter performance and efficacy. The findings from this study will be used to provide additional preliminary data to BD to support a National Institutes of Health or Agency for Healthcare Research and Quality (AHRQ) application (pending 2017 AHRQ funding announcements). Stakeholder feedback will be provided through an optional de-identified report to all patients and families.

Presentation of data

It is anticipated that the results from this study will be presented to American Society for Apheresis at their annual convention. The results will also be summarized in a manuscript and submitted for peer-review publication to Journal of Clinical Apheresis.

Appendix 1

Patient Sticker

A Randomized Trial Examining Plasma Exchange using the BD Catheter In an Outpatient Apheresis Unit The "REPLACE" study

Date SID Procedure Type						

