Instructions:	Please complete the following form except for the VAS scale. Must be completed by patient to measure the characteristics of pain severity. Please circle option that apply.					
Collect CBC	Yes	Νο				
Catheter type	18 GA BD Autogard	20 GA BD Nexiva Diffusics				
Vein diameter w/tourniquet:	Vein diameter w/o turniquet:	Vein diameter Procedure Running:				
Asses pain after return placement						
Please rate your current pain by drawing a vertical line across the bar below						

vere		Extremely Severe		
		Procedure d	ata	
tart time:				
Inlet rate	Return line pressures	Alarms	Comments	
	tart time:	tart time: Inlet rate Return line	Procedure da tart time: Inlet rate Return Alarms line	

Total Procedure time:	Procedure en	Procedure end time:		Final Inlet Volume/Blood Processed:	
Collect post proceduer Plasma Hemoglobin	Yes		No		

References

- Golestaneh, L., & Mokrzycki, M. H. (2013). Vascular access in therapeutic apheresis: update 2013. *Journal of clinical apheresis, 28*(1), 64-72.
- Kalantari, K. (2012). The choice of vascular access for therapeutic apheresis. *Journal of clinical apheresis*, 27(3), 153-159.
- Keller, S. C., Williams, D., Rock, C., Deol, S., Trexler, P., & Cosgrove, S. E. (2018). A new frontier: Central line–associated bloodstream infection surveillance in home infusion therapy. *American journal of infection control*, 46(12), 1419-1421.
- Kramer, N. (2016). Monitoring Central Line-Associated Bloodstream Infections (CLABSI) in Home Infusion. *Infusion*, 22(4), 35-44.
- McDiarmid, S. (2015). Reduce the risk of infection by reducing the need for central lines: using ultrasound guidance to establish peripheral access in patients with sickle cell disease undergoing red cell exchange apheresis. *Journal of clinical apheresis*, *30*(2), 98-99.

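### Neither efficacy outcome measures treatment delivered, and mean minutes are pooled over procedure types and programmed sizes without adjustment

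*Combined protocol and SAP*

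**What the plan says.** The Statistical Analysis Plan tests a primary hypothesis of same efficacy with no increase in adverse events. It uses ANOVA to explore "efficacy wherein efficacy is represented by 1) the plasma hemoglobin value" and, second, "the amount of time (minutes) required to complete a TAP". The analysis of time is to "compare the mean number of minutes to complete TAP by group"; no covariate, stratum or scaling is named.

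The Study procedure section uses plasma hemoglobin to look for hemolysis. It also says of the procedure itself: "The RN will collect a CBC before the start of the procedure which will be used in the programing of the TAP procedure". Three procedure types are eligible: plasma exchange, red blood cell exchange and photopheresis. The paragraph on quality of apheresis expresses inlet rate as a percentage of the maximum for the procedure type, so that it is comparable across types. It does nothing similar for time.

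Potential Risks names two consequences of a smaller catheter: "Longer procedure time might occur if the inlet rate of the treatment is slower", and "With smaller catheters there's a risk of not obtaining the appropriate return rate for the patient". It then describes the response: after repeated alarms the inlet rate is lowered in steps to a minimum, and if alarms persist the 20-gauge is replaced by the 18-gauge.

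The form in Appendix 1 has a field for "Final Inlet Volume/Blood Processed". Sources of Research Material lists "procedure data (minutes, inlet rate, return line pressures and alarms) total procedure time and post procedure sample" and does not mention volume. No comparison between arms uses volume.

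**The concern.** A catheter gives the same efficacy if the patient receives the same treatment. Plasma hemoglobin speaks to harm, and minutes speak to duration. Equal means on both are compatible with equal delivery and also with lower delivery in one arm. The plan does not define a completed procedure, and it does not say how a procedure that stops short, or one switched to the 18-gauge, is counted.

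Separately, minutes depend on the type of procedure and on how it was programmed that day, as well as on the catheter. Comparing raw means leaves all of that variation in the error term with only 33 encounters per arm. The pilot is meant to refine and power a full trial, so a poorly specified efficacy outcome and an inflated standard deviation would both be carried forward.

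**Working it through.** **Inputs from the documents.** 33 encounters per group (Concise Summary of Project). Maximum inlet rates of 100, 55 and 50 for plasma exchange, red cell exchange and photopheresis (quality of apheresis paragraph). Minimum rates of 50, 35 and 20 in the same order (Potential Risks). Only ratios of these rates are used. The plan's one relevant figure is 33 + 33 = 66; it gives no alpha, power, effect size or standard deviation, so nothing further can be reproduced.

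**Assumptions.** Volumes, stopping shares and coefficients of variation (CV) below are assumed. Encounters are treated as independent, although a patient may contribute up to ten.

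**1. Slow flow lengthens time.** Take minutes = volume processed / inlet rate. For the same volume, minimum against maximum rate gives:
- plasma exchange: 100/50 = 2.0 times as long
- red cell exchange: 55/35 = 1.57 times
- photopheresis: 50/20 = 2.5 times

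So where the full volume is processed, raw minutes register a slow catheter clearly.

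**2. A shortfall offsets it.** A run wholly at the minimum rate takes the same minutes as a full run at the maximum rate if it processes 50/100 = 50%, 35/55 = 64% or 20/50 = 40% of the volume. These are extreme cases that show the identity at work.

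**3. Break-even.** If the 20-gauge rate is lower by a fraction s, and a share q of its procedures stop at volume fraction v, mean time relative to 18-gauge is [1 − q(1 − v)]/(1 − s). This equals 1 when q = s/(1 − v).
- s = 0.10, v = 0.50: q = 0.20, or 6.6 of 33
- s = 0.10, v = 0.75: q = 0.40, or 13.2 of 33
- s = 0.20, v = 0.50: q = 0.40, or 13.2 of 33

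**4. Worked example (assumed).** 18-gauge: 5.0 L in 100 min, 20.0 min/L. 20-gauge: 22.0 min/L, so 110 min if complete; 6 of 33 stop at 3.0 L after 66 min.
- Mean 20-gauge time: (27 × 110 + 6 × 66)/33 = 3366/33 = 102 min. The 10-minute slowing shows as 2.
- If the six complete at the same rate, the mean is 110 min and the full 10 minutes show.
- Minutes per litre: 110/5.0 = 66/3.0 = 22.0. The slowing shows, but a 60% procedure scores the same as a complete one.
- Mean percentage of volume delivered: (27 × 100 + 6 × 60)/33 = 92.7%, with 27/33 = 82% completed. Only these show the shortfall.

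A simulation of 20,000 trials (volume CV 0.20, residual CV 0.15) agrees. With no rate difference and 20% of 20-gauge procedures stopped at half volume, mean minutes were 92.9 against 103.2, while time per unit volume was 101.1 in both arms.

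**5. Precision without any shortfall.** A 10% lower rate makes time longer by 1/0.9 − 1 = 0.111 of the mean. With volume CV 0.20 and residual CV 0.15, the CV of raw minutes is √(0.20² + 0.15² + 0.20² × 0.15²) = 0.252. With 33 per arm and two-sided alpha 0.05, power is 43% for raw minutes and 85% if variation in volume is removed completely. The simulation gave 38% and 80%. For volume CV from 0.10 to 0.40, the formula gives raw-minutes power from 70% down to 18%.

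The standard error of the chance difference in mean volume between arms is CV × √(2/33): 2.5% of the mean at CV 0.10 and 9.8% at CV 0.40. It is centred on zero.

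**The case against.** The strongest case against is the protocol's own failure pathway. A 20-gauge that cannot sustain flow has its rate lowered and is then exchanged for an 18-gauge. Nothing says that a catheter-limited procedure is ended early, and longer time is the stated risk. A reader might infer that the plan rewards procedures cut short, or that time is biased toward the 20-gauge. The documents do not support that: on the written pathway a poor catheter normally costs minutes, and the outcome would usually show it. The wording of the outcome can also be read as covering completed procedures only.

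A reader might likewise infer that smaller programmed procedures bias the comparison. Each encounter is randomised, so programmed size and procedure type balance on average. Bias would need programming or stopping to differ by arm. The treating nurse knows the catheter, so this is possible, but no text indicates it.

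It can further be said that inlet rate is already a standardised quality measure, that the plan will summarise every variable, and that this is an exploratory pilot. These points moderate the concern without closing it. Inlet rate is not volume delivered, and no between-arm analysis of it is specified in the Statistical Analysis Plan. A general summary of each variable is not a comparison of volume by arm. If completion is required, dropping incomplete procedures would select on an event after randomisation that may depend on the catheter. Replacing the catheter does not guarantee that the programmed volume is then reached.

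**Conclusion.** The concern holds as a gap in the efficacy outcomes and a loss of precision. It does not hold as a demonstrated bias toward the 20-gauge. The plan can conclude same efficacy without evidence that the programmed treatment was delivered, although volume processed is on the form.

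The size of any masking depends on how often procedures end below their programmed volume, which the documents do not give. With no such procedures, masking is nil. Under the assumed stopping of 6 in 33 at 60%, 8 of 10 minutes of slowing disappear. The precision loss does not depend on early stopping, but its size rests on the assumed CVs; the 85% figure is a best case in which volume variation is removed entirely. That programming sets a target volume is an inference from the statement that the CBC is used in programming.

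**What to change.** 1. Add a delivered-treatment efficacy outcome to the Statistical Analysis Plan, compared by randomised arm: final volume processed as a percentage of the volume programmed at the start. Add the programmed volume to the form, in the same quantity and unit as the existing field. Count a procedure ending below that volume as not completed, and keep it in its randomised arm.
2. Keep total minutes as an outcome. Count encounters switched to the 18-gauge in the arm to which they were randomised, and adjust for procedure type and programmed volume. Read this result beside outcome 1, since adjustment for programmed volume does not correct the short time of an incomplete procedure.
3. Report minutes per litre processed only as supportive, and only within or stratified by procedure type. It does not detect under-delivery, and with maximum rates of 50, 100 and 55 it can differ about two-fold between types.

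The cost is one extra form field, a few sentences in the plan and a little more analysis. No clinical procedure changes.

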To accomplish these goals, our outpatient clinic is open Monday thru Friday offering 4 different appointment times. All patients that are referred to our clinic for TAP, first receive a vein evaluation to see if the patient is a candidate for peripheral IV therapy. At our clinic, approximately 68% of our TAP's are performed peripherally. This eliminates the risk of a central line infection and any alteration in activities of daily living, such as bathing(Kramer, 2016), (Shang, Ma, Poghosyan, Dowding, & Stone, 2014),(Keller et al., 2018; McDiarmid, 2015).

Our hypothesis, is that the 20-gauge BD Nexiva Diffusics catheter provides the same efficacy as current practice with no increase in adverse events for patients undergoing therapeutic apheresis. The results from our study will be significant because if the 20 guage needle is equally effective for TAP, it can increase the number of patients that would be candidates for peripheral therapy. Therefore, decreasing the need for central venous access, which place the patient at an increased risk of infection. Our study is a comparison of 2 types of infusion catheters. The standard of care is an 18-gauge autogard catheter (control group) which will be compared to the 20-gauge BD Nexiva Diffusics (intervention).

- P patients who require therapeutic apheresis procedures (TAP)
- I use of 20G BD diffusics catheter during apheresis
- C use of 18 G standard of care IV catheter during apheresis
- O no difference in efficacy and no increase in safety events

Concise Summary of Project

This is a randomized pilot study of TAP using the current standard of care catheter (SOC) vs the BD Nexiva Diffusics Catheter. It is a single blinded, randomized study. Data will be used to refine and power a full randomized control trial. For this study, a sample of 33 encounters in each group (total of 66 encounters). Our specific aim is to test the hypothesis that the 20-gauge BD Nexiva Diffusics Catheter provides the same efficacy and lower pain level with no increase in adverse events for patients undergoing apheresis treatments.

Randomization Procedure

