After an eligible participant is consented to the study the patient will be randomized without replacement to the use of one of the two catheters. Using a random number generator, numbers between (1-66) were randomly divided into two groups: SOC Control group and BD Intervention group (Figure 1). A study identification number (SID) key will be saved on a UTSW approved secure device and only the research coordinator will have access to the SID key showing which SID coordinates with each group. This will ensure that unblinding can occur is necessary and there is a backup to randomization.

The research coordinator will have 66 randomized envelops without replacement. Half of the envelops will be assigned to 18G catheter SOC (control) and the other half be assigned to

20G BD Nexiva Diffusics catheter (intervention). The PI will be blinded, therefore the PI will pick an envelope when patients are consented and ready for treatment. Participants will be randomized after they have consented to the study. Participants' will then be randomized to one of the two groups again at each encounter (i.e., SOC visit). Inside the envelope it will tell the investigator if the patient is in the control or intervention group of the study.

To promote a more representative sample, each patient may participate a maximum of 10 times.

Study procedure:

[figure not shown]
Each enrolled patient will participate in the study will be randomized at each encounter. During each encounter the following information will be captured:

- 1. CBC
- 2. Patient discomfort

level with placement of catheter

- 3. Inlet rate
- 4. Return line pressures
- 5. Procedures alarms
- 6. Procedure total time
- 7. Post procedure sample

Treating nurse (RN) will start the TAPs procedure with one of the 2 catheters. During the intervention period, the RN will be at bedside during as it is SOC in the Apheresis unit however for the purpose of this study the RN will have the study data collection form (DCF, Appendix1). The RN will complete the pre-assessment including a pain assessment to establish pain level prior to procedure that is currently documented in the electronic medical record. The patient will be asked to self-report the pain level after the return line has been started on the visual analog scale (VAS) Scale from 0mm to 100mm "0 being the lowest/ no pain, 100mm being the highest

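### The by-group ANOVAs of plasma hemoglobin and minutes name no patient or procedure term, which can cost precision, and the adverse-event ANOVA should be worded per encounter

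*Combined protocol and SAP*

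**What the plan says.** The Concise Summary of Project plans "a sample of 33 encounters in each group (total of 66 encounters", and states the purpose of the pilot: "Data will be used to refine and power a full randomized control trial". Under Randomization Procedure, participants "will then be randomized to one of the two groups again at each encounter", and "each patient may participate a maximum of 10 times". Recruitment Methods and Consenting Process expects 30 participants. The Inclusion Criteria admit plasma exchange, red cell exchange and photopheresis.

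The Study procedure section recognises that the three procedures differ. It expresses inlet rate as a percentage of each procedure's maximum, because "this will allow standardization across procedures". It gives no such treatment to the two efficacy endpoints. For those, the Statistical Analysis Plan uses ANOVA to "compare the mean plasma hemoglobin values by group, and to compare the mean number of minutes to complete TAP by group", and names no other term.

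The second step of the primary analysis is an ANOVA of the mean number of adverse events that subjects have in each group. The unit is not stated, although for one safety outcome the Study procedure section is explicit: "Hemolysis will be scored dichotomously as present or absent for each encounter".

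**The concern.** Repeat encounters from one patient are likely to resemble each other, and minutes are likely to differ between procedures. A by-group ANOVA leaves both sources of variation in the error term. Because the catheter varies within patients, a model with a patient term can use within-patient contrasts, and a procedure term can remove differences between procedures. Without them, the interval for the catheter difference may be wider than the same 66 encounters allow.

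The plan also asks the pilot to inform the power of a full trial, but as written it yields no within-patient SD and no ICC.

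For adverse events, a patient with encounters in both arms belongs to neither group alone, and may have more encounters in one arm than in the other. A per-subject mean by group therefore has no common denominator. This comparison is half of the primary hypothesis.

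**Working it through.** **Inputs from the documents.** 2 × 33 = 66 encounters, which agrees with the stated total; 30 expected participants, so 66/30 = 2.2 encounters each; a cap of 10, so at least 7 patients (66/10 = 6.6, rounded up); three procedures. The documents give no ICC, SD, run times, procedure mix or spread of encounters over patients. These are assumed below.

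**Type I error of the ANOVA.** With 33 of 66 encounters allocated at random, two encounters of one patient fall in the same arm with probability 32/65 and in different arms with probability 33/65. Coding the arms ±1, the expected product is (32 − 33)/65 = −1/65, so positive correlation within patients does not inflate the variance of the group difference. Simulation with a common catheter effect agrees: rejection rates were 4.3 to 5.4% over ICC 0.2 to 0.8 and 7 to 30 patients.

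**Patient term.** The simulation permuted 33/33 over 66 encounters. Each of 30 patients had at least one encounter, with the rest spread at random up to the cap. The random-intercept model estimated the ICC by REML. The variance ratio is mixed model over ANOVA, and the change in standard error (SE) is √ratio − 1. The ANOVA 95% half-width is t(0.975, 64) × √(2/33) = 1.998 × 0.246 = 0.492 SD, which is then multiplied by √ratio.

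| Assumed ICC | Variance ratio | Change in SE | Half-width (SD) |
|---|---|---|---|
| 0 | 1.02 | +1% | 0.50 |
| 0.1 | 1.00 | 0 | 0.49 |
| 0.3 | 0.91 to 0.94 | −5% to −3% | 0.47 to 0.48 |
| 0.5 | 0.73 | −14% | 0.42 |
| 0.7 | 0.47 to 0.49 | −31% to −30% | 0.34 to 0.35 |

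Ranges show repeat simulations. The half-widths keep 64 degrees of freedom, so Kenward-Roger intervals would be slightly wider. In other layouts (15, 20 or 45 patients, or 4 patients with 10 encounters and 26 with one), the ratio is 0.84 to 0.96 at ICC 0.3 and 0.62 to 0.86 at ICC 0.5.

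**Procedure term, minutes.** If procedure explains a share R² of the variance, the SE falls by about 1 − √(1 − R²): 11, 23 and 37% at R² = 0.2, 0.4 and 0.6. Simulation with three equally common procedures, fixed within patient, gives 10, 21 and 36%. With both terms at a within-procedure ICC of 0.3, the cut is about 12, 24 and 40%.

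**Plasma hemoglobin.** The documents describe no procedure effect. If there is none, the procedure term costs 0.3 to 1.5% of the SE, and both terms together change the SE by +2, −3 and −12% at ICC 0, 0.3 and 0.5.

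**If the catheter effect varies between patients.** With an assumed effect SD of 0.5 and ICC 0.5, rejection of a zero mean effect is about 6, 7 and 12% for ANOVA with 30, 15 and 7 patients. For the random-intercept model with a fixed cut-off it is about 7, 11 and 16%.

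**Precision of the ICC.** With 30 patients, the middle 95% of estimates runs from 0 to 0.58 at a true ICC of 0.3, and from 0.18 to 0.72 at 0.5.

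**Adverse-event unit.** A patient with m encounters is in both arms with probability 1 − 2·C(66 − m, 33)/C(66, 33): 0.51 for m = 2, 0.76 for m = 3 and 0.999 for m = 10. In the 30-patient layout about 46% of patients are in both arms, and about 53% of those have unequal numbers. Across the layouts the share in both arms is 13 to 83%.

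**The case against.** The strongest reply is that the by-group comparison is a legitimate exploratory analysis in a pilot. The plan speaks of constructing models and does not rule out covariates, procedure type is already on the Appendix 1 form, and the gain depends on values that nobody knows. Much of this stands. At low ICC there is no gain, and for plasma hemoglobin the procedure argument has no support in the documents. What remains is that a plan should name its terms in advance, and that the terms cost little if they prove idle.

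A reader might infer more than the documents support, in four ways:

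- **The ANOVA is invalid because of repeated patients.** Allocation is by encounter, so with a common catheter effect type I error stays near 5%. If the effect varies between patients this fails, but the random-intercept model then fails at least as badly, so it is not a remedy.
- **The adverse-event comparison cannot be run.** Group belongs only to the encounter, each arm has 33 encounters, and hemolysis is scored per encounter. The encounter is therefore the natural reading, and the wording needs repair, not the design. Stating the unit does not, however, settle which events are counted.
- **Patient identity is lost.** Randomization Procedure mentions "the SID key showing which SID coordinates with each group", which could suggest one number per envelope. But Procedures to Maintain Confidentiality gives the number to participants and links it to names, and the form carries a patient sticker. Identity is recoverable.
- **A narrower interval would show equal efficacy.** No margin is stated, so precision alone cannot establish that.

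**Conclusion.** The point holds as one of specification and efficiency, and the change is a cheap improvement worth making. Conditional on a common catheter effect, the ANOVA is valid and its cost is precision. With 30 patients that cost is nil at ICC 0 to 0.1, about 3 to 5% of the SE at 0.3 and about 14% at 0.5. For minutes the larger gain may come from procedure type, but its 10 to 36% rests on assumed variance shares of 20 to 60%. None of these inputs can be taken from the documents. The adverse-event wording is a real but easily cured ambiguity. The ICC and within-patient SD are worth reporting for the later trial, although 66 encounters will estimate them poorly.

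**What to change.** In the Statistical Analysis Plan:

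- Analyse each efficacy endpoint at encounter level, with randomised catheter and procedure type as fixed effects, a patient random intercept, and Kenward-Roger or Satterthwaite degrees of freedom.
- Report the catheter difference with its 95% CI, and the within-patient SD and ICC with their intervals, noting that these will be imprecise.
- State that the type I error of this analysis assumes a catheter effect common to all patients.
- Reword the adverse-event comparison as events per encounter by arm, with clustering by patient, or as a table per encounter if events are few.
- Carry a patient identifier, distinct from the envelope number, into the analysis dataset.

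The cost is wording, a few lines of SAS and one column. No new patient data are needed. The statistical downside is an SE about 2% wider if neither term explains variance. If the catheter effect does vary between patients, the model can also be more anti-conservative than ANOVA: about 7% against 6% with 30 patients, and 16% against 12% with 7, under the assumptions above and a fixed cut-off.
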